4.4 Timing of interim analyses

Given the adaptive enrollment model and signal finding nature of this study, frequent interim analyses may be required to inform futility, early success (go/no-go decisions), and final success declarations within the tumor cohorts. The first interim analysis for the primary endpoint will occur when one or more tumor cohorts have accrued 5 patients with 24 week CBR data. Subsequent interim analyses will occur when at least 10 additional patients enrolled to the study

have 24 week CBR data available AND at least 3 months have elapsed since the previous interim analysis cut off. Interim analyses for primary endpoint will continue at minimum 3 month intervals until end of study (provided at least 10 additional patients have 24 week CBR data at each interim analysis).

There is no plan for a formal interim analysis of safety or other secondary endpoints for this study. However, for publication or other purposes, interim data review of clean data will be performed as necessary. At these interim reviews, patient demographics/baseline characteristics, the primary and secondary endpoints as applicable, and all important safety endpoints will be summarized. No formal report will be issued for these data reviews.

4.5 Early study termination

The study can be terminated at any time for any reason by Novartis. Should this be necessary, the patient should be seen as soon as possible for End of Treatment (EOT) visit and the same assessments for EOT should be performed as described in [Section 7](#) for a discontinued or withdrawn patient. The investigator may be informed of additional procedures to be followed in order to ensure that adequate consideration is given to the protection of the patient's interests. The investigator will be responsible for informing IRBs and/or ECs of the early termination of the trial.

5 Population

5.1 Definition of End of Study

Patient accrual to the study will end when all tumor cohorts have completed initial futility and expansion analysis AND all expanded cohorts have accrued 30 patients. The study will end when all enrolled patients have either discontinued or completed 2 years of study therapy AND 150 days of safety follow up.

5.2 Patient population

This study will be conducted in 35-210 patients with select solid tumors or hematological malignancies as outlined in [Table 4-1](#). Tumor types may be excluded or added during the course of the study in the case of early futility or success based upon an interim analysis or at the discretion of Novartis.

Patients enrolled in this study are not permitted to participate in additional parallel investigational drug or device studies.

The investigator or designee must ensure that only patients who meet all the following inclusion and none of the exclusion criteria are offered treatment in the study.

5.3 Inclusion criteria

Patients eligible for inclusion in this study have to meet **all** of the following criteria:

1. Written informed consent must be obtained prior to any screening procedures.
2. Patient is \geq 18 years of age on the day of consenting to the study

3. Patient must have had at least one prior line of therapy for their disease and must not be beyond 4th progression/relapse of disease (5 maximum prior lines).
4. Patient has a pathology confirmed diagnosis of a solid tumor or lymphoma listed in [Table 4-1](#) and measurable disease as per appropriate guidelines:
 - **All Solid Tumors: by RECIST 1.1 (Appendix 1)**
 - For advanced well differentiated neuroendocrine tumors, the following also apply:
 - Pathologically confirmed, well-differentiated (Grade 1 or Grade 2), advanced (unresectable or metastatic), neuroendocrine tumor
 - No history of and no active symptoms related to carcinoid syndrome
 - Patient has not had hepatic intra-arterial embolization within the last 6 months or cryoablation or radiofrequency ablation of hepatic metastases within 2 months of first dose
 - **Diffuse Large B-cell Lymphoma: by the Revised Response Criteria for Malignant Lymphoma (Cheson et al 2007) (Appendix 2)**
 - Relapsed/refractory disease as defined by relevant standardized response criteria (see [Section 4](#))
 - Patients with prior autologous transplant are eligible
 - Patient has at least one measurable nodal lesion (≥ 2 cm). In case where the patient has no measurable nodal lesions ≥ 2 cm in the long axis at screening, then the patient must have at least one measurable extra-nodal lesion
5. Patient has an Eastern Cooperative Oncology Group (ECOG) performance status ≤ 1
6. Patient must have locally advanced or metastatic disease.

5.4 Exclusion criteria

Patients eligible for this study must not meet **any** of the following criteria:

1. Presence of symptomatic CNS metastases, or CNS metastases that require local CNS-directed therapy (such as radiotherapy or surgery), or increasing doses of corticosteroids within the prior 2 weeks. Patients with treated brain metastases should be neurologically stable (for 4 weeks post-treatment and prior to study enrollment) and off steroids for at least 2 weeks before administration of any study drug.
2. History of severe hypersensitivity reactions to other mAbs
3. Patient with out of range laboratory values:
 - a. Creatinine clearance (calculated using Cockcroft-Gault formula, or measured) < 40 mL/min
 - b. Total bilirubin $> 1.5 \times$ ULN, except for patients with Gilbert's syndrome who are excluded if total bilirubin $> 3.0 \times$ ULN or direct bilirubin $> 1.5 \times$ ULN
 - c. Alanine aminotransferase (ALT) $> 3 \times$ ULN, except for patients that have tumor involvement of the liver, who are excluded if ALT $> 5 \times$ ULN
 - d. Aspartate aminotransferase (AST) $> 3 \times$ ULN, except for patients that have tumor involvement of the liver, who are excluded if AST $> 5 \times$ ULN

- e. Absolute neutrophil count (ANC) $< 1.0 \times 10^9/L$
- f. Platelet count $< 75 \times 10^9/L$
- g. Hemoglobin $< 9 \text{ g/dL}$
4. Impaired cardiac function or clinically significant cardiac disease, including any of the following:
 - a. Clinically significant and/or uncontrolled heart disease such as congestive heart failure requiring treatment (NYHA Grade ≥ 2), uncontrolled hypertension or clinically significant arrhythmia
 - b. QTcF $> 470 \text{ msec}$ on screening/baseline ECG or congenital long QT syndrome
 - c. Acute myocardial infarction or unstable angina pectoris < 3 months prior to study entry
5. Active, known or suspected autoimmune disease or a documented history of autoimmune disease within three years prior to screening with exception of:
 - a. Patients with vitiligo, type I diabetes mellitus, residual hypothyroidism due to an autoimmune condition only requiring hormone replacement, psoriasis not requiring systemic treatment, or conditions not expected to recur in the absence of an external trigger are permitted to enroll.
6. If otherwise eligible for the IO sub-group, patients previously exposed to anti-PD-1/PD-L1 treatment who are adequately treated for skin rash or with replacement therapy for endocrinopathies should not be excluded
7. Active infection requiring systemic antibiotic therapy. Patients requiring systemic antibiotics for infection must have completed therapy before screening is initiated.
8. Known history of HIV infection. Testing for HIV status is not necessary unless clinically indicated
9. Active hepatitis B virus (HBV) or hepatitis C virus (HCV) infection. Testing for HBV or HCV status is not necessary unless clinically indicated or the patient has a history of HBV or HCV infection.
10. Patient with second primary malignancy within < 3 years of first dose of study treatment. Exceptions to this exclusion include the following: malignancies that were treated curatively and have not recurred within 2 years prior to study treatment; completely resected basal cell and squamous cell skin cancers; any malignancy considered to be indolent and that has never required therapy; and completely resected carcinoma in situ of any type.
11. Any medical condition that would, in the investigator's judgment, prevent the patient's participation in the clinical study due to safety concerns, compliance with clinical study procedures or interpretation of study results.
12. Systemic anti-cancer therapy within 2 weeks of the first dose of study treatment. For cytotoxic agents that have major delayed toxicity, e.g. mitomycin C and nitrosoureas, 4 weeks is indicated as washout period.
13. Prior immunotherapy treatment with PD-1, PD-L1, CTLA-4, or LAG-3 antibodies, CAR-T therapy, gene therapies, and/or Provenge therapy.
 - a. This exclusion does not apply to patients enrolled in the immunotherapy pre-exposed subgroup (n=6 per tumor type) in those cohorts that undergo expansion to 30 patients.

b. For patients in the immunotherapy pre-exposed subgroups:

- Prior IO therapy with PD-1, PD-L1, or LAG-3 antibodies, within 4 weeks of first dose of study treatment
- CTLA-4 antagonist or vaccine as anticancer therapy within 6 weeks of first dose of study treatment
- Patients who discontinued prior anti-PD-1, PD-L1 or anti LAG-3 therapy due to therapy related toxicity
- Patients with a history of any grade immune-related ocular adverse event.
- Patients with a history of Grade ≥ 3 immune-related adverse event.
- Patients with evidence of active noninfectious pneumonitis or history of interstitial lung disease.
- Patients with risk of reactivation of hepatitis B or C.
- Patients who are on endocrine replacement therapy should be stable on the dose.

14. Systemic chronic steroid therapy or any immunosuppressive therapy (>10 mg/day prednisone or equivalent). Topical, inhaled, nasal and ophthalmic steroids are allowed.

15. Use of any live vaccines against infectious diseases within 4 weeks of initiation of study treatment.

16. Use of hematopoietic colony-stimulating growth factors (e.g. G-CSF, GM-CSF, M-CSF) or erythroid stimulating agents ≤ 2 weeks prior to start of study drug. If erythroid stimulating agents were initiated more than 2 weeks prior to the first dose of study treatment and the patient is on a stable dose, they can be maintained.

17. Presence of CTCAE \geq grade 2 toxicity (except peripheral neuropathy and ototoxicity, which are excluded if \geq CTCAE grade 3) due to prior cancer therapy.

18. Allogeneic stem cell transplant recipients

19. Major surgery within 2 weeks of the first dose of study treatment (mediastinoscopy, insertion of a central venous access device, and insertion of a feeding tube are not considered major surgery).

20. Participation in an interventional, investigational study within 2 weeks prior to the first dose of study treatment.

21. Pregnant or lactating women, where pregnancy is defined as the state of a female after conception and until the termination of gestation, confirmed by a positive hCG laboratory test.

22. Women of child-bearing potential, defined as all women physiologically capable of becoming pregnant, unless they are using highly effective methods of contraception during dosing and for 150 days after the last dose of PDR001 and LAG525. Women are considered post-menopausal and not of child bearing potential if they have had 12 months of natural (spontaneous) amenorrhea with an appropriate clinical profile (i.e. age appropriate, history of vasomotor symptoms) or have had surgical bilateral oophorectomy (with or without hysterectomy), total hysterectomy, or tubal ligation at least six weeks ago. In the case of oophorectomy alone, only when the reproductive status of the woman has been confirmed by follow up hormone level assessment is she considered not of child bearing potential.

- a. Highly effective contraception methods include:
- b. Total abstinence (when this is in line with the preferred and usual lifestyle of the subject). Periodic abstinence (e.g., calendar, ovulation, symptothermal, post-ovulation methods) and withdrawal are not acceptable methods of contraception.
- c. Female sterilization (have had surgical bilateral oophorectomy with or without hysterectomy), total hysterectomy, or tubal ligation at least six weeks before taking study treatment. In case of oophorectomy alone, only when the reproductive status of the woman has been confirmed by follow up hormone level assessment.
- d. Male sterilization (at least 6 months prior to screening). The vasectomized male partner should be the sole partner for that subject.
- e. Use of oral, injected or implanted hormonal methods of contraception or placement of an intrauterine device (IUD) or intrauterine system (IUS), or other forms of hormonal contraception that have comparable efficacy (failure rate <1%), for example hormone vaginal ring or transdermal hormone contraception.
- f. In case of use of oral contraception women should have been stable on the same pill for a minimum of 3 months before taking study treatment.

23. Sexually active males unless they use a condom during intercourse while taking the drug and for 150 days after stopping study treatment and should not father a child in this period. A condom is required to be used also by vasectomized men as well as during intercourse with a male partner in order to prevent delivery of the drug via seminal fluid.

6 Treatment

6.1 Study treatment

[REDACTED] All dosages prescribed and dispensed to patients and all dose changes during the study must be recorded on the Dosage Administration Record eCRF.

6.1.1 Dosing regimen

Table 6-1 Dose and treatment schedule

Study treatments	Pharmaceutical form and route of administration	Dose	Frequency and/or Regimen
PDR001	[REDACTED]	[REDACTED]	Every 3 weeks (Q3W)
LAG525	LAG525 [REDACTED]	[REDACTED]	Every 3 weeks (Q3W)

[REDACTED]

[REDACTED]

6.1.2 Ancillary treatments

[figure not shown]
Patients should not receive pre-medication to prevent infusion reactions before the first infusion of study treatment, in order to determine if pre-medication is necessary. If a patient experiences an infusion reaction, he/she may receive pre-medication on subsequent dosing days. The pre-medication should be chosen per institutional standard of care, at the discretion of the treating physician. Acute allergic reactions should be treated as needed per institutional standard of care. In the event of anaphylactic/anaphylactoid reactions, this includes any therapy necessary to restore normal cardiopulmonary status. If a patient experiences a Grade 3 anaphylactic/anaphylactoid reaction, the patient will be discontinued from the study. The patient may resume study treatment following documented discussion with the Novartis medical monitor.

Guidelines on management of infusion reactions are provided in [Table 6-3](#).

The CTCAE category of “Infusion related reaction” should be used to describe study treatment related infusion reactions, unless the investigator considers another category, such as “Allergic reaction,” “Anaphylaxis,” or “Cytokine release syndrome” more appropriate in a specific situation.

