6.3 Dose modifications

6.3.1 Dose modification and dose delay

Dose reductions are not permitted. PDR001 and LAG525 may be delayed due to toxicities. The dosing regimen may resume once the adverse event has resolved to grade 1 or baseline, and the start of the cycle will be shifted accordingly.

If the Investigator considers it to be in the patient's best interest to resume therapy before the toxicity has resolved to Grade 1 this may be permitted, following documented discussion with the Novartis medical monitor.

Overall, irAEs that do not recover to \leq Grade 1 or baseline at a dose of immunosuppression of ≤ 10 mg/day prednisone or equivalent (or as indicated in the [Table 6-2](#)) within 12 weeks after initiation of immunosuppressive therapy, PDR001 and LAG525 must be permanently discontinued. All interruptions or changes to study drug administration must be recorded on the Dose Administration Record eCRF.

If PDR001 and LAG525 treatment is interrupted for more than 12 weeks due to study treatment-related toxicities, then the study treatment should be permanently discontinued. If a patient who misses more than 12 weeks of study treatment has objective evidence of response (e.g. serum, urine, or marrow evidence of response that does not meet criteria for PR, or documented improvement in a physical exam finding), and in the opinion of the investigator it is in the patient's best interest to remain on study, then the patient may continue study treatment following documented approval from Novartis. Details are provided in [Table 6-2](#) below.

Table 6-2 Maximum permitted missed doses prior to permanent discontinuation of study treatment

Study drug	Maximum permitted missed consecutive doses prior to permanent discontinuation of study treatment
------------	--

PDR001	3
LAG525	3

Patients who discontinue the study for a study related AE or a study-related abnormal laboratory value must be followed as described in [Section 6.3.2](#). All interruptions or change to study drug administration must be recorded on the Dose Administration Record eCRF.

Dose delays for adverse events related to the study medication are summarized in [Appendix 5](#). Generally, following resolution of the adverse event to Grade 1 or to the patient's baseline value, the patient may resume study treatment on the same dosing schedule, if there is no evidence of disease progression.

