frequently if required by institutional practices, or if clinically indicated) for 4 weeks, and subsequently at approximately 4-week intervals, until resolution or stabilization of the event, whichever comes first. All patients must be followed up for irAEs, AEs and SAEs for 150 days following the last dose of study treatment.

Table 6-3 outlines the recommended dose delays and follow-up evaluations for selected toxicities.

Table 6-3 Recommended Dose Delays and re-initiation of treatment for adverse drug reactions

Worst Toxicity CTCAE v4.03 Grade	Recommended Dose Delays
Cardiac disorders	
ECG QTc-Interval prolonged Grade 2 (except myocarditis)	Hold study treatment. Upon resolution to Grade ≤ 1 or baseline, may resume study treatment without dose modification after discussion with the Novartis Medical Monitor.
Grade 2 myocarditis,	Discontinue study treatment
Grade 3	Omit dose of LAG525 and PDR001 until returned to CTCAE Grade ≤ 1 or < 30 msec difference from baseline. Baseline ECG refers to the ECG(s) collected at screening. May resume study treatment without modifications after discussion with Novartis Medical Monitor.
Grade 4	Discontinue study treatment.
Cardiac disorders – others	
Grade 1 and 2	Maintain dose level of LAG525 and PDR001.
Grade ≥ 3	Discontinue study treatment.
Skin toxicity	
Rash/photosensitivity Grade 1	Maintain dose level of LAG525 and PDR001 and manage per institutional standard guidelines. (Topical steroids, antihistamines, topical emollients)
Grade 2	Consider holding study treatment. Topical or oral steroids, antihistamines. If study treatment is held and resolution to ≤ Grade 1, resume study treatment without dose modification.
Grade 3 or Grade 4	hold dose of LAG525 and PDR001 until returned to CTCAE Grade ≤ 1. Treat according to institutional practice which generally includes anti-histamine regimen, corticosteroid treatment (oral or topical) can be considered for symptomatic rash (e.g. pruritus). consider resuming therapy after expert consultation and documented discussion with Novartis Medical Monitor.
Bullous dermatitis	

Worst Toxicity CTCAE v4.03 Grade	Recommended Dose Delays

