Grade 2	Stop infusion immediately, and keep line open. Provide supplemental oxygen and fluids, as needed. Monitor vital signs (e.g., blood pressure, pulse, and temperature) every 15 ± 5 minutes until resolution. Administer medications for symptomatic relief as needed: Urticaria: Diphenhydramine (25 to 100 mg i.v.) as needed every 4 to 6 hours, or alternative as appropriate. Fever: Acetaminophen/paracetamol (650-1000 mg by mouth) as needed every 4 to 6 hours, or alternative as appropriate. Rigors: Meperidine 25 mg i.v. as needed every 6 hours or alternative as appropriate. Corticosteroids may be administered, as needed. Resume infusion once infusion reaction resolves (within 8 hours of initial start of infusion): Maintain dose level. Administer oral pre-medication (e.g. 1000 mg of acetaminophen/paracetamol, 50-100 mg diphenhydramine hydrochloride or alternative antihistamine), within 60 minutes of restarting the infusion. Restart infusion at 50% of previous rate under continuous observation. Ensure that there is a minimum observation period of 1 hour prior to restarting the infusion. - If the AE recurs at the reinitiated slow rate of infusion, and despite oral pre-medication, then discontinue patient from study treatment.
Grade 3 or 4	Discontinue infusion immediately, and permanently discontinue patient from study treatment. Provide supplemental oxygen, fluids, and other resuscitative measures as needed. Guidance provided above. Monitor vital signs (e.g., blood pressure, pulse, respiration, and temperature) every 15 ± 5 minutes until resolution.
Type 1 Diabetes mellitus	Monitor patients for hyperglycemia or other signs and symptoms of diabetes and diabetic ketoacidosis. Administer insulin for type 1 diabetes. In patients with severe hyperglycemia omit dose of LAG525 and PDR001 and manage as per Institutional guidelines until resolved to ≤ Gr 1
Cytokine Release Syndrome (CRS)	
Grade 2	See Instructions for Grade 2 Infusion Reactions.
Grade 3 or Grade 4	Discontinue study treatment Follow-up CRS as per institutional guidelines.

Worst Toxicity CTCAE v4.03 Grade	Recommended Dose Delays
Ocular (uveitis, eye pain, blurred vision)	
Grade 1	Continue study treatment without dose modification. Ophthalmology consultation.
Grade 2	Hold study treatment. Urgent ophthalmology consultation. Upon resolution to ≤ Grade 1 may consider resuming study treatment without dose reduction after discussion with the Novartis Medical Monitor and in consultation with ophthalmology.

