Grade 3 or Grade 4	Discontinue study treatment. Urgent ophthalmology consultation.
Renal	
Serum Creatinine	
Grade 2	Hold study treatment. Manage per institutional practice. Upon resolution to ≤ Grade 1, may resume study treatment without dose modification after discussion with the Novartis Medical Monitor.
Grade 3 or 4	Discontinue Study Treatment
Musculoskeletal	
Grade 2 or Grade 3	Hold study treatment. Consider resuming study treatment without dose modification upon resolution to ≤ Grade 1 with appropriate management.
Grade 4	Discontinue study treatment In some cases, resuming study treatment may be considered after discussion with the Novartis Medical Monitor and consultation with a rheumatologist.
Endocrine	
Hypothyroidism or hyperthyroidism	
Grade 2	May continue study treatment without dose modification. Management according to institutional practice.
Grade 3	Hold Study Treatment Upon resolution to Grade ≤ 1 with appropriate management, may resume study treatment without dose modification.
Grade 4	Hold Study Treatment. May resume study treatment following resolution or control with physiologic hormone replacement
Other Endocrine Disorders	
Grade 2 and Grade 3	Hold study treatment. Upon resolution to Grade ≤ 1 with appropriate management, may resume study treatment without dose modification.
Grade 4	Hold study treatment. Grade 4 treatment-related endocrinopathies, such as adrenal insufficiency, adrenocorticotrophic hormone (ACTH) deficiency, hyper- or hypothyroidism, or glucose intolerance, which resolve or are adequately controlled with physiologic hormone replacement (corticosteroids, thyroid hormones) or glucose-controlling agents, respectively, may not require discontinuation after discussion with and approval from the Novartis Medical Monitor.
Neurology	
Grade 1	Consider study treatment hold, particularly for clinical

Worst Toxicity CTCAE v4.03 Grade	Recommended Dose Delays
Grade 2	suspicion of Guillain-Barre syndrome, encephalitis, aseptic meningitis, transverse myelitis, or peripheral neuropathy. Hold study treatment. In some cases, resuming study treatment may be considered after discussion with the Novartis Medical Monitor.
Grade 3 or Grade 4	Discontinue study treatment.
Hematology	
Neutropenia (ANC) Grade 3 or Grade 4	Hold study treatment. Upon resolution to ≤ Grade 2 or baseline within ≤ 7 days, resume study treatment without dose modification, after discussion with the Novartis Medical Monitor.

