7.1.5 Discontinuation of study treatment

Patients may voluntarily discontinue from the investigational treatment for any reason at any time. If a patient decides to discontinue, the investigator should make a reasonable effort (e.g. telephone, e-mail, letter) to understand the primary reason for this decision and record this information in the patient's chart and on the appropriate CRF pages. They may be considered withdrawn if they state an intention to withdraw, fail to return for visits, or become lost to follow-up for any other reason.

The investigator should discontinue investigational treatment for a given patient if he/she believes that continuation would be detrimental to the patient's well-being.

Study treatment may be discontinued if any of the following occur:

- Adverse event
- Lost to follow-up
- Physician's decision
- Progressive disease per defined response criteria
- Study terminated by the sponsor
- Subject/guardian decision
- Protocol deviations that result in significant risk to the patients' safety
- Technical problems

Patients will be withdrawn if any of the following occur:

- Pregnancy
- Death

At the time patients discontinue study treatment, a visit should be scheduled as soon as possible, and within 14 days of the last dose of study drug or within 14 days of the decision to permanently discontinue study treatment, at which time all of the assessments listed for the EOT visit will be performed ([Table 7-1](#)). If the decision to withdraw the patient occurs at a regularly scheduled visit, that visit may become the EOT visit rather than having the patient return for an additional visit. An End of Treatment Phase Disposition CRF page should be completed, giving the date and reason for stopping the study treatment. End of treatment/Premature withdrawal visit is not considered as the end of the study.

At a minimum, all patients who discontinue study treatment, including those who refuse to return for a final visit, will be contacted for safety evaluations during the 150 days following the last dose of study treatment.

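### Protocol 6.1.2 allows a return to study drug after a Grade 3 anaphylactic reaction, while the Table 6-3 infusion-reaction row it points to makes Grade 3 or 4 a permanent stop

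*Protocol*

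**What the plan says.** Protocol section 6.1.2 (Ancillary treatments) deals with infusion and allergic reactions. For a Grade 3 anaphylactic or anaphylactoid reaction it says that "the patient will be discontinued from the study. The patient may resume study treatment following documented discussion with the Novartis medical monitor". It does not mention Grade 4. It then refers the reader to Table 6-3 for the management of infusion reactions. It also says that a treatment-related infusion reaction is normally recorded under the CTCAE infusion-reaction category, but that the investigator may judge another category more fitting. Allergic reaction, anaphylaxis and cytokine release syndrome are given as examples.

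Table 6-3 (section 6.3.2) has an infusion-reaction block. Its Grade 3 or 4 entry reads: "Discontinue infusion immediately, and permanently discontinue patient from study treatment". The rest of the entry covers supportive care and vital-sign monitoring. It has no exception and no route back through the medical monitor.

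Three general provisions also bear on the point:

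- Section 6.3.1 on dose delays: "The dosing regimen may resume once the adverse event has resolved to grade 1 or baseline". The next paragraph relaxes this. If the investigator thinks it in the patient's interest to "resume therapy before the toxicity has resolved to Grade 1 this may be permitted, following documented discussion with the Novartis medical monitor".
- Section 6.3.2 on follow-up: "All patients must be followed up for irAEs, AEs and SAEs for 150 days following the last dose of study treatment".
- Section 7.1.5 on stopping: "The investigator should discontinue investigational treatment for a given patient if he/she believes that continuation would be detrimental" to the patient's well-being.

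**The concern.** A site facing a severe reaction during an infusion needs one answer to whether the patient may ever receive the drugs again. Here it can find two. Section 6.1.2 leaves the way back open after a conversation with the sponsor's monitor. The table that the same section cites closes it.

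What is at stake is re-exposure, to the same antibodies, of a patient who has already had a severe reaction to them. The protocol treats this kind of risk as serious elsewhere: exclusion criterion 2 in section 5.4 keeps out patients with a history of severe hypersensitivity to other monoclonal antibodies, and section 2.6 lists allergic reactions among the possibly serious events with the combination.

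Sites also cannot settle the conflict by asking permission to depart from one of the rules, because section 12 rules out authorised deviations.

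**Working it through.** No arithmetic applies, so the check is a comparison of the texts.

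**1. Do the two rules give different answers?**

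| | Section 6.1.2 | Table 6-3, infusion reactions |
|---|---|---|
| Event named | Anaphylactic or anaphylactoid reaction | Infusion reaction |
| Grade | 3 | 3 or 4 |
| Action | Discontinued from the study | Study treatment permanently discontinued |
| Route back to drug | Yes, after documented monitor discussion | None stated |

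They differ at Grade 3. At Grade 4, section 6.1.2 is silent, so there is no direct conflict.

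**2. Can one event fall under both?** Yes. Section 6.1.2 offers anaphylaxis as an alternative label for a treatment-related infusion reaction, and it sends infusion reactions to Table 6-3. If the event is recorded as an infusion-related reaction, the table's permanent stop applies. If the same event is recorded as anaphylaxis, a reader can rely on the resumption sentence in 6.1.2.

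**3. Is an exception implied in the table row?** The table's own drafting suggests not. Where a stop has a way back, the row says so. The musculoskeletal Grade 4 entry discontinues treatment and then adds: "In some cases, resuming study treatment may be considered after discussion with the Novartis Medical Monitor and consultation with a rheumatologist". The entry for severe bilirubin elevation likewise spells out an exception for the indirect component. The infusion-reaction entry has nothing similar. Grade 3 or 4 cytokine release syndrome, another of the alternative labels in 6.1.2, has its own entry and is also a stop with no return route.

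**4. Does another provision say which rule controls?**

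- The 6.3.1 resolution rule says when dosing may restart after a delay. It does not say whether a permanent stop can be reversed.
- The 6.3.2 rule on resuming after a DLT, or after severe or serious suspected immune-related events, requires a monitor discussion. It names neither infusion reactions nor anaphylaxis.
- The catch-all entries at the end of Table 6-3 might apply if anaphylaxis is treated as an event the table does not list. The other non-laboratory Grade 3 entry holds treatment and requires a monitor discussion after resolution to Grade 1 or better. The closing note on remaining Grade 3 or higher events allows a less frequent schedule, after consulting the sponsor, if the event resolves within 21 days. Whether either applies is arguable, because 6.1.2 points to the infusion-reaction entries and the first catch-all also excludes events covered by the consensus guidelines.

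None of these settles the order of precedence.

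**5. Is 6.1.2 consistent within itself?** No. A patient discontinued from the study cannot then resume treatment in it. The wording also does not match the follow-up rule, under which safety follow-up continues for 150 days after the last dose.

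**The case against.** The strongest reply is that the rules cover different events. Table 6-3 does not name anaphylaxis. The list of alternative labels in 6.1.2 includes cytokine release syndrome, which has its own table entry, so being on that list does not by itself place an event under the infusion-reaction row. On this reading 6.1.2 is the specific rule for anaphylaxis and the row governs other infusion reactions. It stands to this extent: the link to the row is inferred. It does not remove the problem, because it would give the more dangerous label the more lenient rule.

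A second reply is that both texts begin by stopping treatment, that nothing resumes without a documented discussion in which the monitor can apply Table 6-3, and that the protocol describes the table as guidelines and recommendations. The gate is real, and so is the investigator's duty in 7.1.5. But the row is worded without condition, and a monitor reading the protocol finds the same two answers as the site.

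A reader might go further than the documents allow in two ways:

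- One might infer that, beyond the discussion, the waivable 6.3.1 rule is the only condition on re-challenge. The catch-all entries arguably add conditions, so a count of conditions would not be reliable.
- One might infer that re-challenge is more loosely controlled after Grade 3 than after Grade 2, since the Grade 2 entry says "Restart infusion at 50% of previous rate under continuous observation" and adds other steps. That entry governs restarting the same infusion within hours. A later decision to re-treat is a different matter, so the comparison is not like for like.

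The phrase about discontinuation from the study is loose wording with no shown consequence for follow-up: 6.3.1 uses a similar phrase and still requires it.

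**Conclusion.** The inconsistency is real and should be corrected. At Grade 3, section 6.1.2 permits a re-exposure that the table row it refers to forbids, and the choice of CTCAE category could decide which rule a patient meets. The existing safeguards are partial and do not say which rule controls.

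The conclusion assumes that a Grade 3 anaphylactic or anaphylactoid reaction to the infusion is an infusion reaction for the purposes of Table 6-3. The cross-reference and the category list in 6.1.2 make this the natural reading, though the table does not say it outright.

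The scope is narrow: one grade of one type of event. The documents give no frequency for these reactions or for re-challenge, so the number of patients affected cannot be estimated. This is a patient-safety point only. It has no effect on the primary analysis.

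**What to change.** In the next amendment:

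1. Delete the sentence in 6.1.2 that allows resumption.
2. State there that a Grade 3 or 4 anaphylactic or anaphylactoid reaction to the infusion leads to permanent discontinuation of study treatment under Table 6-3, with the 150-day safety follow-up continuing. This also replaces the wording about discontinuation from the study.
3. Name anaphylactic and anaphylactoid reactions in the Grade 3 or 4 infusion-reaction row of Table 6-3, so that the category chosen no longer matters.

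The cost is one sentence and one table row. The downside is that a rare patient loses the option of monitor-approved re-challenge. Whether to keep that option is a clinical choice. If the sponsor wants it, the exception and its conditions belong in the table row, where the table's other exceptions are written. The two places need to be reconciled in either case.
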